13.1.4 Safety Analysis

For all safety endpoints, Baseline is defined as the last non-missing measurement prior to first dose of study drug. All safety analyses will be summarized using the safety analysis set.

13.1.4.1 AEs

All AEs will be coded by system organ class, high level term, and preferred term using MedDRA. TEAEs are defined as AEs with onset occurring within 30 days (onset date – last date of dose +1≤30) after study drug administration. TEAEs will be summarized by treatment group and dosing frequency by system organ class and preferred term. The following summary tables will be included in the report: summary of TEAEs and drug-related TEAEs, relationship of TEAEs to study drug (related vs. not-related), severity of TEAEs and related TEAEs. Data listings will be provided for all AEs including PTE, TEAEs, AEs leading to study drug discontinuation, and SAEs.

13.1.4.2 Safety Laboratory Evaluation

Individual results of safety laboratory tests from hematology, chemistry, and urinalysis that meet Takeda's markedly abnormal criteria will be summarized and listed. Baseline, postdose, and change from Baseline to postdose laboratory data will be summarized. All clinical laboratory data will be listed.

13.1.4.3 Vital Signs

Individual results of vital signs that meet Takeda's markedly abnormal criteria will be summarized and listed. Baseline, postdose, and changes from Baseline in vital sign measurements will be summarized. All vital sign data will be provided in the data listings.

13.1.4.4 ECGs

Individual results of qualitative ECG parameters from the 12-lead safety ECGs that meet Takeda's markedly abnormal criteria will be summarized and listed. Shift tables will be generated for the investigator's ECG interpretations that changed from Baseline to the postdose collections. All ECG data will be provided in the data listings.

13.2 Interim Analysis and Criteria for Early Termination

No interim analysis is planned.

13.3 Determination of Sample Size

A sample size of at least 77 subjects in each treatment group (total of 154 subjects) is needed to detect a difference between Placebo and CER 15 mg in subject's rating of medication helpfulness impression, using a 2-sample Wilcoxon rank sum test with 80% power at a 2-sided significance level of 0.05 (Kolassa, J. E. (1995), "A Comparison of Size and Power Calculations for the Wilcoxon Statistic for Ordered Categorical Data," *Statistics in Medicine*, 14, 1577–1581). The assumed difference to be detected is based on the observed distribution of the ordinaly scored rating scale for the respective treatment groups in study 1106. Assuming a 15% dropout rate, 90 subjects in each treatment group (total of 180 subjects) will be randomized.

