6.2 Justification for Study Design, Dose, and Endpoints

- Study design including primary and secondary criteria for evaluation and methods of measurement will be similar to previous pivotal Cyclobenzaprine studies in order to determine positive efficacy trend of Cyclobenzaprine 15 mg versus Placebo;
- The randomized, double-blind, parallel, placebo-controlled design will reduce bias in different treatment regimens with respect to efficacy and safety. Randomization will provide maximum assurance that subject characteristics are similar across the treatment groups. Blinding subjects and all study personnel who will be involved in their assessment to the study treatment will maintain the objectivity of the assessment;
- A placebo arm has been added, since the primary endpoint is a subjective score and the placebo control allows to better evaluate the treatment effect of Cyclobenzaprine;
- A placebo arm is acceptable because the study is of short duration and the cervical and/or lower back pain due to muscle spasms is not considered a life-threatening condition if untreated. Moreover, rescue therapy will be implemented in lack of efficacy cases before subject is discontinued from the study;
- The dose level of Cyclobenzaprine 15 mg once daily is chosen for this study as the approved dose for the treatment of the pain due to muscle spasms of local origin. The Cyclobenzaprine 15 mg once daily has shown its efficacious and safe in adult patients with the pain due to muscle spasms, so it is expected that the same dose will be effective and safe in Russian patients.

The endpoint assessment for this study will take place on Day 3 instead of Day 4 (as utilized in 1105 and 1106 studies) which is based on cyclobenzaprine MR 30 mg pharmacokinetic parameters T_{max}

= 10.5 ± 3.32 hours and $t_{1/2} = 27.7 \pm 8.56$ hours and implies capturing probable earlier clinical effects of the drug than it was shown in previous studies.

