9.3.2 Randomization

Randomization will take place on Day1 (could be the same day at which Screening visit took place). The following procedures will be performed and documented during Randomization:

- Vital Signs (if not same day as Screening procedures).
- Concomitant medications.
- Adverse Events.
- The following parameters will be assessed by the investigator: presence of muscle spasm, presence of local pain, limitation of activities of daily living, and limitation of range of motion.
- Subject Diary dispense. Subjects should be instructed :
 - To complete assessment for Day 1 at the hospital before the first drug intake.
 - Starting from Day 2 record the following assessments (compared to Baseline) in the daily diary: rating of medication helpfulness, relief from local pain, subject-rated Clinical global impression, restriction in activities of daily living, and restriction of movement;
 - To record the following assessments in the daily diary: **Company Confidential Information** intensity of local pain **Company Confidential Information** ;
 - To complete their diary during 14 days at the same time each day if possible but record the worst feeling/symptom since the diary was last completed. No diary to be completed at Day 15 (Visit 4) but returned to the Investigator.
 - To bring their diary to each study visit for review by Investigator. Completed pages will be collected by Investigator, then the diary will be dispensed to subject again.
- If the subject has satisfied all of the inclusion criteria and none of the exclusion criteria for randomization, the subject should be randomized using the IVRS/IWRS, as described in Section 8.2.
- Study drug dispense. The medication identification (ID) number of the study drug will be provided via IVRS/IWRS. To avoid any overdose and non-compliance with study drug intake, original bottle containing 60 capsules with CER 15 mg or Placebo will be opened in front of the subject and 40 capsules of 60 will be removed in cleanliness condition and put into the additional bottle for keeping at the site (never dispensed to subject) until destruction. Original bottle containing 20 capsules with CER 15 mg or Placebo will be dispensed to subject. Subject will be instructed to:
 - To swallow one capsule whole with 180 mL of room temperature water, once daily in the evening between 18:00 and 19:00 starting from Day1.

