Hard gelatin capsules with blue to blue-green body with white imprint “1002-30” and red to red-orange cap with white imprint “EUR”. Capsule content - white to yellow spherical granules.

Pharmacotherapeutic group: Central muscle relaxant

ATC code: M03BX08

Pharmacological properties

Pharmacodynamics

Cyclobenzaprine cures skeletal muscle spasm not affecting muscle function. Animal studies showed that cyclobenzaprine does not directly affect neuromuscular transmission or directly skeletal muscles. Cyclobenzaprine reduced or eliminated skeletal muscle hypertension on animal models. Data of the studies also showed that cyclobenzaprine primarily affects central nervous system at cerebral trunk level. Inhibition of neuromuscular transmission at the level of spinal cord also plays role in general myorelaxing effect on skeletal muscles. Data available indicate that direct effect of cyclobenzaprine is reduction of tonic somatic motor activity by affecting both gamma (γ)- and alpha (α)-motor systems. Pharmacological studies on animals demonstrated similar effect of cyclobenzaprine and structurally related tricyclic antidepressants, including antagonism in relation to reserpine, potentiation of noradrenaline, express peripheral and central anticholinergic effect and sedation. Cyclobenzaprine induced slight to moderate increase of heart rate in animal studies.

Pharmacokinetics

Absorption

After single administration of cyclobenzaprine in a dose of 15 mg and 30 mg by healthy volunteers (n = 15), dose-dependent increase of C_{max} , AUC_{0-168h} and AUC_{0-∞} has been observed. Maximum cyclobenzaprine concentration in blood plasma is reached in 7 - 8 hours for both dosages.

Cyclobenzaprine pharmacokinetics does not depend on food ingestion. C_{max} value increases to 35%, AUC increases to 20%, however first concentrations of cyclobenzaprine in blood plasma are observed in 1.5 hour, with or without food.

In multiple dose study with administration of 30 mg of cyclobenzaprine once a day within 7 days in a group of healthy volunteers (n = 35) with steady state concentration, 2.5 fold increase of cyclobenzaprine concentration in blood plasma has been observed.

Metabolism and excretion

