Cyclobenzaprine to a great degree is metabolized and excreted primarily in the form of glucuronides by urinary way. Cytochrome isoenzymes P-450 3A4, 1A2, and to a lesser degree, 2D6, mediate N-demethylation - one of oxidation ways of cyclobenzaprine metabolism. Elimination half-time of cyclobenzaprine - 32 hours (8- 37 hours range; n = 18); total body clearance - 0.7 L/min after single drug dose administration.

Elderly patients (65 years old and over)

Despite that fact, that no significant difference in C_{max} or T_{max} has been observed, AUC of plasma cyclobenzaprine increased to 40%, cyclobenzaprine elimination half-time was longer in elderly patients at the age of 65 years and more (50 hours) compared to younger patients at the age of 18 -45 years (32 hours). Pharmacokinetics of cyclobenzaprine after multiple dose administration of drug in elderly patients was not evaluated.

Patients with liver function abnormality

In pharmacokinetics study of cyclobenzaprine immediate release in 16 patients with liver dysfunction (15 slight, 1 moderate based on Child – Pugh scores), both AUC, and C_{max} were approximately twice higher compared to values in healthy control group. Pharmacokinetics of cyclobenzaprine in patients with severe liver dysfunction has not been observed.

Indications for use:

Myorix® is indicated as therapeutic appliance for acute pain control in case of muscle spasm, induced by disorders of locomotor system. Drug effect is based on elimination of muscle spasm and its symptoms, i.e. pain syndrome and limited excursion.

Myorix® should be used only during a short period (up to two-three weeks), as long as data on the drug efficiency with longer administration are unavailable, and also due to that fact, that muscle spasm, related to locomotor system disorders usually has short duration and specific treatment for more than three weeks is rarely reasonable.

It was found that Myorix® is not efficient for treatment of muscle spasms induced by disorders of central nervous system, and also with cerebral palsy in children.

Contra indications:

- hypersensitivity to cyclobenzaprine or other drug components;
- children under 18 years;
- coadministration with monoaminooxidase inhibitors (MAO) and administration within 14 days after their withdrawal.
- recent myocardial infarction, fibrillation, AV block or other asequences, congestive heart failure, unstable angina;
- hyperthyroidism.

Administration during pregnancy and breastfeeding

Pregnancy

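### Does sizing a Day 3 endpoint on the difference seen in study 1106, which was assessed on Day 4, undermine the stated 80% power?

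*Protocol*

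**What the plan says.** Section 13.3 asks for at least 77 subjects per group for a two-sample Wilcoxon rank sum test with 80% power at two-sided 0.05. It raises this to 90 per group for 15% dropout. The difference to be detected is "based on the observed distribution of the ordinaly scored rating scale for the respective treatment groups in study 1106". Neither the category percentages nor the day they refer to is given.

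Section 6.2 explains the timing: "The endpoint assessment for this study will take place on Day 3 instead of Day 4 (as utilized in 1105 and 1106 studies". It says the choice "implies capturing probable earlier clinical effects of the drug than it was shown in previous studies", and the supporting figures are a Tmax of 10.5 ± 3.32 h and a half-life of 27.7 ± 8.56 h, "which is based on cyclobenzaprine MR 30 mg pharmacokinetic parameters".

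Section 9.3.2 has the capsule taken "once daily in the evening between 18:00 and 19:00 starting from Day1". The Day 1 diary entry is made at the hospital before the first capsule, and later entries at the same time each day where possible. Completed pages are collected at the Day 3 visit (Section 9.3.3).

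Appendix E gives a half-life of 32 h (range 8 to 37 h). On the peak it says: "Maximum cyclobenzaprine concentration in blood plasma is reached in 7 - 8 hours for both dosages". After seven daily 30 mg doses, "2.5 fold increase of cyclobenzaprine concentration in blood plasma has been observed".

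**The concern.** The two sections do not obviously fit together. If the 1106 distribution is the Day 4 one, Section 13.3 borrows a Day 4 difference for a Day 3 test without comment, while Section 6.2 presents effects earlier than those already shown as probable only.

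The reason for moving to Day 3 is pharmacokinetic, yet the drug is still accumulating at that point. With evening dosing from Day 1, a subject has taken two capsules before a daytime Day 3 visit and would have taken three by the same hour on Day 4. The figures offered for the earlier day thus imply lower exposure on it. They are also for 30 mg, while the trial gives 15 mg, and they differ somewhat from Appendix E.

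Power is what is at stake. The efficacy claim in a registration trial rests on one Day 3 test, and a smaller true difference on that day would raise the chance of missing a real effect. Type I error and the validity of the test are not affected.

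**Working it through.** **The stated sample size.** The 77 cannot be recomputed, because the 1106 category percentages are not in the protocol. It can be back-solved. With z-values 1.960 and 0.842 (sum 2.802), 77 per group corresponds to a standardized difference of √(2 × 2.802² / 77) = 0.45. By Noether's formula without ties, that is a probability of about 0.63 that a treated subject rates higher than a placebo subject. Dropout: 77 / 0.85 = 90.6, against 90 stated; 90 × 0.85 = 76.5. That is rounding.

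**Exposure.** For once-daily dosing with linear kinetics, let x = 0.5^(24 / half-life). The level after m doses, as a fraction of steady state, is 1 − x^m.

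- 27.7 h (Section 6.2): x = 0.5485. Two doses give 0.699, three 0.835, four 0.909. Ratios: 0.699 / 0.835 = 0.84 and 0.835 / 0.909 = 0.92.
- 32 h (Appendix E): x = 0.5946. Two doses give 0.646, three 0.790, four 0.875. Ratios: 0.646 / 0.790 = 0.82 and 0.790 / 0.875 = 0.90.
- Check on the model: 32 h implies accumulation of 1 / (1 − 0.5946) = 2.47, in line with Appendix E's 2.5-fold.
- Over Appendix E's half-life range of 8 to 37 h, the two-versus-three-dose ratio runs from 0.99 to 0.80.

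Adding first-order absorption fitted to each stated Tmax leaves these reductions nearly unchanged, at 16% to 17% and 18%.

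**Power if the effect is a fraction f of the 1106 effect.** Power = Φ(2.802 × f × √(n / 77) − 1.960).

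| f | Where f comes from | n = 90 | n = 77 |
|---|---|---|---|
| 1.00 | effect not limited by exposure | 85.7% | 80.0% |
| 0.925 | √(77 / 90), break-even at 90 | 80.0% | 73.6% |
| 0.92 | three v four doses, 27.7 h | 79.6% | 73% |
| 0.90 | three v four doses, 32 h | 77.8% | 71% |
| 0.84 | two v three doses, 27.7 h | 72.0% | 65% |
| 0.82 | two v three doses, 32 h | 70.0% | 63% |

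The n = 90 column fits the analysis in Section 13.1.3, which uses everyone dosed and carries the last rating forward. The n = 77 column assumes that the full 15% dropout is lost to the Day 3 test. The last four rows set f equal to the exposure ratio, which nothing in the documents supports or excludes.

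**From exposure to a treatment difference.** Three things in the protocol stand between the ratio and a loss of power.

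1. Section 4.1 says that after oral dosing the effect begins within an hour and that a single dose acts for 12 to 24 hours (formulation not specified). That speaks against an effect that must wait for several days of accumulation.
2. The endpoint is a difference between arms in a condition that Appendix E describes as usually short-lived. Placebo recovery between Day 3 and Day 4 also moves that difference, and less recovery by Day 3 could make it larger.
3. Day 4 is inferred as the source of the 1106 distribution. Section 6.2 says measurement here resembles that in the earlier pivotal studies, and this trial uses a daily diary, so a Day 3 rating from 1106 may exist and may be what was used.

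**The two sets of kinetic figures.** One standard deviation around the Section 6.2 means gives 19.1 to 36.3 h for half-life and 7.2 to 13.8 h for Tmax. Appendix E's 32 h lies inside the first interval and nearly all of its 7 to 8 h inside the second. The choice between half-lives moves the ratio only from 0.84 to 0.82.

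**The case for a change.** The case for a change is serious. The basis of the sample size is fixed in this protocol, so it is not something a later analysis plan would settle. The sponsor chose to move the endpoint, gave only a kinetic reason, and that reason points to lower exposure. It can fairly be said that the sponsor should support f = 1. Two versus three doses is also the more natural reading, since the diary is tied to the hour of the Day 1 hospital entry and its pages are handed over at the visit. The margin between 77 and 90 was meant for dropout; without it, power in the proportional case is 63% to 65%.

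What stands is that Section 13.3 leaves an assumption unstated and that the exposure arithmetic is right. What does not follow is that the 80% is wrong. That needs an effect proportional to plasma level, a Day 4 source for the 1106 distribution, the same dosing schedule in 1106, and a placebo course that does not offset the loss. None of these is in the documents.

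The possible changes fail for the same reason. Enlarging to 77 / 0.84² = 109.1 (110) or 77 / 0.82² = 114.5 (115) evaluable per group would spend subjects on the proportionality assumption. Making Day 4 primary would reverse a disclosed choice to look for an earlier effect. Naming the 1106 day and percentages would make the calculation easier to audit, and reconciling the kinetic figures would tidy Section 6.2, but neither alters the design, the analysis or any result.

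**Conclusion.** No change follows. Moving the endpoint a day earlier than in the reference study is a stated design choice, and the missing day in Section 13.3 is a gap in reporting. It is not evidence of a wrong sample size. Exposure on Day 3 is 16% to 18% below Day 4 if the rating precedes the evening dose and 8% to 10% below if it follows, given linear kinetics and the same once-daily schedule in 1106. Under strict proportionality, power at 90 per group would be 70% to 72% or 78% to 80% respectively. With no dependence on exposure it would be 86%, and the target is met as long as at least 92.5% of the 1106 effect is present on Day 3. The documents do not place the trial within that range. The Day 3 comparison keeps its type I error either way, and the same analysis is repeated at Days 7 and 14, so a later effect would still be described.

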14.0 CONTROL AND QUALITY ASSURANCE

14.1 Study-Site Monitoring Visits

Monitoring visits to the study site will be made periodically during the study to ensure that all aspects of the protocol are followed. Source documents will be reviewed for verification of data recorded on the (e)CRFs. Source documents are defined as original documents, data, and records. The investigator and institution guarantee access to source documents by the sponsor or its designee (CRO) and by the IRB or IEC.

All aspects of the study and its documentation will be subject to review by the sponsor or designee (as long as blinding is not jeopardized), including but not limited to the Investigator's Binder, study medication, subject medical records, informed consent documentation, documentation of subject authorization to use personal health information (if separate from the informed consent forms), and review of (e)CRFs and associated source documents. It is important that the investigator and other study personnel are available during the monitoring visits and that sufficient time is devoted to the process.

14.2 Protocol Deviations

The investigator should not deviate from the protocol, except where necessary to eliminate an immediate hazard to study subjects. Should other unexpected circumstances arise that will require deviation from protocol-specified procedures, the investigator should consult with the sponsor or designee (and IRB or IEC, as required) to determine the appropriate course of action. There will be no exemptions (a prospectively approved deviation) from the inclusion or exclusion criteria.

The site should document all protocol deviations in the subject's source documents. In the event of a significant deviation, the site should notify the sponsor or its designee (and IRB or EC, as required). Significant deviations include, but are not limited to, those that involve fraud or misconduct, increase the health risk to the subject, or confound interpretation of primary study assessment. A Protocol Deviation Form should be completed by the site and signed by the sponsor or designee for any significant deviation from the protocol.

14.3 Quality Assurance Audits and Regulatory Agency Inspections

The study site also may be subject to quality assurance audits by the sponsor or designees. In this circumstance, the sponsor-designated auditor will contact the site in advance to arrange an auditing visit. The auditor may ask to visit the facilities where laboratory samples are collected, where the medication is stored and prepared, and any other facility used during the study. In addition, there is the possibility that this study may be inspected by regulatory agencies, including those of foreign governments (eg, the FDA, the United Kingdom Medicines and Healthcare products Regulatory Agency, the Pharmaceuticals and Medical Devices Agency of Japan). If the study site is contacted for an inspection by a regulatory body, the sponsor should be notified immediately. The investigator and institution guarantee access for quality assurance auditors to all study documents as described in Section 14.1.

15.0 ETHICAL ASPECTS OF THE STUDY

This study will be conducted with the highest respect for the individual participants (ie, subjects) according to the protocol, the ethical principles that have their origin in the Declaration of Helsinki, and the ICH Harmonised Tripartite Guideline for GCP. Each investigator will conduct the study according to applicable local or regional regulatory requirements and align his or her conduct in accordance with the “Responsibilities of the Investigator” that are listed in Appendix B. The principles of Helsinki are addressed through the protocol and through appendices containing requirements for informed consent and investigator responsibilities.

15.1 IRB and/or IEC Approval

IRBs and IECs must be constituted according to the applicable federal/local requirements of each participating region. The sponsor or designee will require documentation noting all names and titles of members who make up the respective IRB or IEC. If any member of the IRB or IEC has direct participation in this study, written notification regarding his or her abstinence from voting must also be obtained.

The sponsor or designee will supply relevant documents for submission to the respective IRB or IEC for the protocol’s review and approval. This protocol, the Investigator’s Brochure, a copy of the informed consent form, and, if applicable, subject recruitment materials and/or advertisements and other documents required by all applicable laws and regulations, must be submitted to a central or local IRB or IEC for approval. The IRB’s or IEC’s written approval of the protocol and subject informed consent must be obtained and submitted to the sponsor or designee before commencement of the study (ie, before shipment of the sponsor-supplied drug or study specific screening activity). The IRB or IEC approval must refer to the study by exact protocol title, number, and version date; identify versions of other documents (eg, informed consent form) reviewed; and state the approval date. The sponsor will ship drug once the sponsor has confirmed the adequacy of site regulatory documentation and, when applicable, the sponsor has received permission from competent authority to begin the trial. Until the site receives drug no protocol activities, including screening may occur.

Sites must adhere to all requirements stipulated by their respective IRB or IEC. This may include notification to the IRB or IEC regarding protocol amendments, updates to the informed consent form, recruitment materials intended for viewing by subjects, local safety reporting requirements, reports and updates regarding the ongoing review of the study at intervals specified by the respective IRB or IEC, and submission of the investigator’s final status report to IRB or IEC. All IRB and IEC approvals and relevant documentation for these items must be provided to the sponsor or its designee.

Subject incentives should not exert undue influence for participation. Payments to subjects must be approved by the IRB or IEC and sponsor.

